5.14. Safety Evaluation

5.14.1. Exposure

Exposure to study drug will be analyzed for all patients treated with any non-zero amount of study drug. Analyses will be summarized for the treated subset of the ITT population and the treated subset of the LMS population. A summary of study drug exposure will include number of infusions, duration of therapy, cumulative dose level, weekly dose intensity, and relative dose intensity. The exposure formulas of olaratumab and doxorubicin are defined below.

Olaratumab:

- Duration of therapy (in weeks) = $([\text{Date of last cycle Day 1} - \text{date of first dose of olaratumab}] + 21) \div 7$
- Cumulative dose (mg) = Sum of all doses
- Calculated dose level administered (mg/kg) = Actual total dose of olaratumab (mg) / Closest body weight prior to that administration (kg)
- Cumulative dose level (mg/kg) = sum of all calculated dose level
- Dose intensity (mg/kg/week) = (cumulative dose level) \div (duration of treatment)
- Planned dose intensity (mg/kg/week) = planned dose per infusion (mg/kg) / infusion cycle
- Relative dose intensity (%) (based on planned dose) = (dose intensity/planned dose intensity)*100

All analyses of olaratumab exposure will be performed for both overall treatment period as well as for monotherapy after the completion of combination treatment with doxorubicin.

Doxorubicin:

- Duration of therapy (in weeks) = $([\text{date of last dose of doxorubicin} - \text{date of first dose of doxorubicin}] + 21) \div 7$
- Cumulative dose (mg) = sum of all doses
- Calculated dose level administered (mg/ m²) = actual total dose of doxorubicin (mg)/closest BSA prior to that treatment (m²)
- BSA (m²) = $[\text{weight (kg)}^{0.425} * \text{height (cm)}^{0.725}] * 0.007184$
- Cumulative dose level(mg/ m²) = sum of all calculated dose levels
- Dose intensity (mg/ m²/weeks) = (cumulative dose level) \div (duration of treatment)
- Planned dose intensity (mg/ m²/weeks) = planned dose per infusion (mg/ m²) / infusion cycle

- Relative dose intensity (%) (based on planned dose) = (dose intensity/planned dose intensity)*100.

Dexrazoxane:

- Duration of therapy (in weeks) = ([Date of last dose of dexrazoxane – date of first dose of dexrazoxane] + 21) ÷ 7
- Calculated dose level administered (mg/m²) = actual total dose of dexrazoxane (mg)/ closest BSA (m²) prior to that treatment
- Cumulative dose (mg) = sum of all doses
- Cumulative dose level (mg/m²) = sum of all calculated dose levels
- Dose intensity (mg/m²/weeks) = (cumulative dose level) ÷ (duration of treatment)
- Planned dose intensity (mg/m²/weeks) = planned dose per infusion (mg/m²) ÷ infusion cycle
- Relative dose intensity (%) (based on planned dose) = (dose intensity/planned dose intensity)*100.

Details of study drug administration will be included in patient listings.

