9.4. Selection and Timing of Doses

A cycle is defined as an interval of 21 days (up to 3 days delay of a cycle will be permitted due to holidays, weekends, bad weather, or other unforeseen circumstances and will not count as a protocol deviation).

Refer to Section 5.3.1 for the olaratumab dose rationale in this study.

The dose of olaratumab/placebo administered will be determined by measuring the patient's weight in kilograms on Days 1 and 8 of each cycle. The dose of doxorubicin administered will be determined by calculating the patient's body surface area (BSA) at the beginning of each cycle. If the patient's weight does not fluctuate by $\geq 10\%$ (increase or decrease) from the weight used to calculate the prior dose, the olaratumab/placebo dose will not need to be recalculated. A $\pm 5\%$ variance in the calculated total dose will be allowed for ease of dose administration.

Patients will receive combination treatment with olaratumab/placebo + doxorubicin for 8 cycles, followed by olaratumab/placebo as monotherapy until evidence of progressive disease (PD), unacceptable toxicity, death, or other withdrawal criteria are met.

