5.2.1. Definitions of Analysis Variables

Definitions of efficacy, safety, and PRO analysis variables are listed in Section 5.2.1.1, Section 5.2.1.2, and Section 5.2.1.3, respectively. Other variables are listed below alphabetically.

- **Age (years):** $(\text{Informed Consent Date} - \text{Date of Birth} + 1)/365.25$.
Note. Average days in a year = 365.25, reflecting the Julian Year of 3 years with 365 days each and 1 leap year of 366 days. Birth month and day are imputed to be 01 July because only birth year is collected through eCRF.
- **Baseline measurement** is the last non-missing measurement prior to first dose for safety analyses, and the last non-missing measurement prior to randomization for demographic and efficacy analyses.
- **Duration** is calculated as:
 - Duration (days): $(\text{End Date} - \text{Start Date} + 1)$
 - Duration (weeks): $(\text{End Date} - \text{Start Date} + 1)/7$
 - Duration (months): $(\text{End Date} - \text{Start Date} + 1)/30.4375$
Note. Days in months = $(1/12) \times \text{average number of days in a year}$
 - Duration (years): $(\text{End Date} - \text{Start Date} + 1)/365.25$
- **Duration of disease** is defined as months from first diagnosis of cancer to randomization.

- **Measurable disease (Yes/No)** is defined as yes for patients with at least 1 target lesion based on radiographic assessment data collected at baseline. If no target lesions are present, then patients would be categorized as a No.
- **Study Day:** Study day indicates the number of days the patient has been receiving study treatment. It is calculated as assessment date – first dose date + 1 day if the assessment is done on or after the first dose day. If the assessment is done prior to the first dose day, study day will be calculated as assessment date – first dose date. Date of first dose is defined as Study Day 1.

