5.2.1.2. Safety Analysis Variables

Definitions of variables for safety analysis are listed by category and alphabetically within category.

Adverse event (AE)-related variables are listed below:

- **Adverse event (AE)** is defined as any untoward medical occurrence in a patient administered a pharmaceutical product, without regard to the possibility of a causal relationship.

AEs of special interest (AESIs)

AESI for olaratumab:

- Infusion-related reactions (IRRs)

AESI for doxorubicin:

- Cardiac arrhythmias
- Cardiac dysfunction

AESI for the combination of olaratumab and doxorubicin:

- IRRs
- Cardiac arrhythmias
- Cardiac dysfunction

Notes.

Categories of AESI may be modified as the understanding of the safety of the investigational drug increases. The final list of categories will be maintained at both compound and study level and reported in the CSR.

Consolidated AEs are composite AE terms consisting of synonymous PTs to allow meaningful interpretation of the AE data. Consolidated AE categories and PTs will be maintained at compound and/or study level and reported in the CSR.

Serious adverse event (SAE) is any AE that results in one of the following outcomes:

- death
- a life-threatening experience (that is, immediate risk of dying)
- persistent or significant disability/incapacity
- initial or prolonged in-patient hospitalization
- congenital anomaly/birth defect
- considered significant by the investigator for any other reason

Treatment-emergent adverse event (TEAE) is defined as an event that first occurred or worsened in severity after baseline and up to 30-day short-term follow-up visit.

Exposure-related variables are listed below:

- **Number of dose level reductions:** Sum of the number of dose level reductions as reported in the eCRF
- **Dose delays:** As reported in the eCRF
- **Dose withheld/skip (Not Administered):** As reported in the eCRF
- **Dose interruption(intravenous hold due to IRR):** As reported in the eCRF

Olaratumab or placebo treatment:

- Duration of treatment (weeks; 21 days added to duration of treatment because administration is every 3 weeks [on Days 1 and 8 of each 3-week cycle]) = $([\text{Date of last cycle Day 1} - \text{date of first dose}] + 21) \div 7$
- Cumulative dose, dose intensity, and relative dose intensity:
 - Cumulative dose (mg/kg) = Sum of (dose administered at each infusion [mg] \div Last available weight [kg])

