 - Weekly dose intensity (mg/kg/week) = (Cumulative dose) \div (Duration of Treatment [week])
 - Planned weekly dose intensity (mg/kg/week) = $2 \times (20 \text{ mg/kg} + (\text{number of cycles} - 1) \times 15 \text{ mg/kg}) / (\text{number of cycles} \times 3 \text{ weeks})$
 - Relative dose intensity (%) = (Weekly dose intensity) \div (Planned weekly dose intensity) $\times 100$

Doxorubicin treatment:

- Duration of treatment (weeks) = $([\text{Date of last dose} - \text{date of first dose}] + 21) \div 7$
- Cumulative dose, dose intensity, relative dose intensity:
 - Cumulative dose (mg/m²) = Sum of (dose administered at each infusion [mg] \div Last available body surface area [BSA] [m²])
 - Weekly dose intensity (mg/kg/week) = (Cumulative dose) \div (Duration of treatment)
 - Planned weekly dose intensity (mg/m²/week) = $75 \text{ mg/m}^2 / 3 \text{ weeks} = 25 \text{ mg/m}^2/\text{week}$
 - Relative dose intensity (%) = (Weekly dose intensity) \div (Planned weekly dose intensity) $\times 100$

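### SAP 5.14.1 and 5.2.1.2 define planned olaratumab/placebo dose intensity differently; with the 21-day cycle, 5.14.1 shows about 200% for full delivery

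*SAP*

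**What the plan says.** The SAP defines planned dose intensity for olaratumab/placebo in two places.

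- **Section 5.2.1.2** gives a drug-specific formula under "Planned weekly dose intensity (mg/kg/week"): 2 × (20 + (n − 1) × 15) mg/kg divided by n × 3 weeks, where n is the number of cycles. It counts two infusions per cycle and treats Cycle 1 separately. The same section describes the schedule: "administration is every 3 weeks [on Days 1 and 8 of each 3-week cycle"].
- **Section 5.14.1** gives a generic line: "Planned dose intensity (mg/kg/week) = planned dose per infusion (mg/kg) / infusion cycle". It has no factor for two infusions per cycle and no term for Cycle 1. The actual intensity is cumulative dose level divided by duration, and the numerator takes in every infusion: "Cumulative dose level (mg/kg) = sum of all calculated dose level".

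The term *infusion cycle* is not defined. Protocol Section 9.4 says "A cycle is defined as an interval of 21 days".

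Both sections claim to define the variables. Section 5.2.1 states "Definitions of efficacy, safety, and PRO analysis variables are listed in" the subsections that follow, which makes 5.2.1.2 the home of the safety variables. Section 5.14.1 states "The exposure formulas of olaratumab and doxorubicin are defined below". Section 5.14.1 also extends its formulas to a second summary: "All analyses of olaratumab exposure will be performed for both overall treatment period as well as for monotherapy" after combination treatment is complete.

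**The concern.** Relative dose intensity is read on a scale where 100% means that the planned regimen was delivered. The two sections set different denominators for it, and 5.14.1 is the section that specifies the exposure output. On its ordinary reading, 5.14.1 compares two infusions per cycle with a plan of one.

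A table of values near 200% would probably be noticed. Under-delivery is harder to spot, because missed Day 8 infusions bring the figure back toward 100%. Omitted Day 8 infusions are foreseeable: Protocol Section 9.4.1.1 provides for skipping that dose when neutrophils do not recover in time. Dose intensity also goes to the data monitoring committee in the safety interim package (SAP Section 5.17.2).

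**Working it through.** **Inputs.** Planned doses are 20 mg/kg on Days 1 and 8 of Cycle 1, then 15 mg/kg on Days 1 and 8 of later cycles (Protocol Section 9.1). A cycle is 21 days (Protocol Section 9.4). Duration is (Day 1 of last cycle − first dose + 21 days) / 7, which is 3n weeks for a patient on schedule (SAP 5.14.1). Relative dose intensity is actual divided by planned, × 100.

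**The plan's own figure.** The only planned intensity that the SAP states as a number is doxorubicin's, 25 mg/m²/week (5.2.1.2). The generic 5.14.1 line reproduces it: 75 / 3 = 25. Doxorubicin is given once per cycle, so this does not settle how the line applies to a drug given twice per cycle.

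**Actual intensity at full delivery**, 2 × (20 + 15(n − 1)) / (3n):
- n = 1: 40/3 = 13.33 mg/kg/week
- n = 4: 130/12 = 10.83
- n = 8: 250/24 = 10.42
- n = 16: 490/48 = 10.21

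**Section 5.2.1.2.** The planned value is the same expression, so relative dose intensity is 100% at every n.

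**Section 5.14.1.** The planned dose per infusion and the infusion cycle both have to be assumed. Relative dose intensity at full delivery is then:

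| Infusion cycle | Planned dose per infusion | n = 1 | n = 4 | n = 8 | n = 16 |
|---|---|---|---|---|---|
| 3 weeks | averaged over cycles | 200% | 200% | 200% | 200% |
| 3 weeks | 15 mg/kg (15/3 = 5.00 per week) | 267% | 217% | 208% | 204% |
| 3 weeks | 20 mg/kg (20/3 = 6.67 per week) | 200% | 163% | 156% | 153% |
| 1.5 weeks | averaged over cycles | 100% | 100% | 100% | 100% |
| 1.5 weeks | 15 mg/kg (15/1.5 = 10.00 per week) | 133% | 108% | 104% | 102% |
| 1.5 weeks | 20 mg/kg (20/1.5 = 13.33 per week) | 100% | 81% | 78% | 77% |

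Worked case for n = 8, 3 weeks, averaged dose: the average planned dose is (20 + 7 × 15)/8 = 15.625 mg/kg; planned intensity is 15.625/3 = 5.208; and 10.417/5.208 = 200%.

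**Every Day 8 infusion missed, 8 cycles.** Actual intensity is (20 + 7 × 15)/24 = 125/24 = 5.21 mg/kg/week.
- 5.2.1.2: 5.21/10.42 = 50%.
- 5.14.1 with a 3-week cycle: 100% (averaged dose), 104% (15 mg/kg) or 78% (20 mg/kg).

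**Monotherapy summary**, with duration counted from the start of monotherapy: actual 2 × 15/3 = 10; planned under 5.14.1 with a 3-week cycle 15/3 = 5; relative dose intensity 200%. The 5.2.1.2 formula does not fit this period either, because it assumes a loading cycle. For four monotherapy cycles it gives 2 × (20 + 3 × 15)/12 = 10.83, so full delivery would show 10/10.83 = 92.3%.

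**The case against.** The strongest reply is that the 200% depends on two readings that 5.14.1 does not state: an infusion cycle of 21 days and a planned dose averaged over cycles. If averaging is allowed and the infusion cycle means the average time per infusion (1.5 weeks), 5.14.1 gives 100% and agrees with 5.2.1.2. The doxorubicin and dexrazoxane lines do not decide between these readings, because for those drugs the cycle and the time per infusion are both 3 weeks. This stands: the 200% is conditional. It does not rescue the line. Nothing in the SAP states the 1.5-week reading, and the protocol's defined cycle is 21 days. A programmer using a fixed planned dose would not recover 100% at every number of cycles under either interval.

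It can also be argued that 5.2.1.2 governs. Section 5.2.1 assigns safety variables to it, its formula is specific to the drug, and the output list in 5.14.1 uses its name, weekly dose intensity. But that list also uses cumulative dose level, a term from 5.14.1, and 5.14.1 presents its own formulas as the definitions.

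The monotherapy figure assumes that duration restarts with monotherapy, which is the ordinary reading of a monotherapy-only summary. Taken literally, the 5.14.1 duration runs from the first olaratumab dose. With 8 combination and 4 monotherapy cycles that gives 120/36 = 3.33 mg/kg/week, or 67% of 5. This is a further reason to write the monotherapy definition out.

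Finally, a constant factor of two would leave the relative comparison between arms intact. That is true with the averaged dose. With a fixed 15 or 20 mg/kg the distortion changes with the number of cycles, so arms treated for different lengths of time would differ even at full delivery.

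**Conclusion.** The inconsistency is real and the concern holds. The SAP gives two formulas for one required output and does not say which applies. With the 21-day cycle, 5.14.1 gives 200% for full delivery if the planned dose is averaged over cycles. At 1 to 16 cycles the range is 204% to 267% with 15 mg/kg and 153% to 200% with 20 mg/kg as the planned dose. Monotherapy gives 200% when its duration is counted from the start of that period.

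The point is minor. Cumulative dose, absolute dose intensity, infusion counts, omissions, reductions and delays are reported separately (SAP 5.2.1.2 and 5.14.1; Protocol Section 12.2.5). No efficacy test, alpha level or sample size depends on this percentage.

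**What to change.** In SAP Section 5.14.1, replace the olaratumab/placebo planned-intensity line with the 5.2.1.2 formula for the overall treatment period. For the monotherapy summary, state a separate denominator: two infusions per 3-week cycle at the monotherapy dose scheduled in the protocol, with no loading-cycle term. State there also that the numerator and duration cover the monotherapy period only.

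The cost is SAP wording. Data collection and trial conduct are unchanged, and the change takes no position on dosing.

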5.14.2. Adverse Events

An adverse event (AE) is defined as any untoward medical occurrence in a patient administered a pharmaceutical product, without regard to the possibility of a causal relationship.

Treatment-emergent adverse event (TEAEs) are events that first occurred or worsened in severity after baseline and up to 30-day short-term follow-up visit. The MedDRA PT derived from the verbatim term will be used and severity is measured using the grade defined by the National Cancer Institute - Common Terminology Criteria for Adverse Events (NCI-CTCAE).

Study drug-related AEs are AEs that were considered to be at least possibly related to study drug by an investigator. Missing relationship is considered related to all study drugs.

Serious adverse events (SAEs) are any AEs that result in one of the following outcomes:

- death
- initial or prolonged inpatient hospitalization
- a life-threatening experience (that is, immediate risk of dying)
- persistent or significant disability/incapacity
- congenital anomaly/birth defect
- considered important by the investigator for any other reason

AEs of special interest (AESIs)

AESIs are events which have been identified as safety signals during preclinical or early clinical trials or based on class effects of similar drugs. These events will be monitored prospectively in

the clinical developmental program. Each event is defined by a careful assessment and grouping of individual related MedDRA PTs. The list of PTs for AESIs is in [Appendix 2](#).

AESI for olaratumab

- IRRs

AESI for doxorubicin

- Cardiac arrhythmias
- Cardiac dysfunction

AESI for the combination of olaratumab and doxorubicin

- IRRs
- Cardiac arrhythmias
- Cardiac dysfunction

Consolidated AEs include Abdominal Pain, Anemia, Fatigue, Hyperbilirubinaemia, Hypertension, Hypoalbuminaemia, Hypokalaemia, Hypomagnesaemia, Hyponatraemia, Hypoproteinemia, Intestinal Obstruction, Leukocytosis, Leukopenia, Lymphopenia, Mucositis, Neuropathy, Neutropenia, Musculoskeletal pain, Rash, and Thrombocytopenia. Each consolidated AE contains PTs identified as clinically identical or synonymous. The list of PTs for consolidated AEs is in the [Appendix 3](#).

The most current version of MedDRA at time of analysis will be used when reporting AEs by MedDRA terms. Unless otherwise specified, when summarized by PT, AEs will be presented in decreasing frequency of PT across treatment arms; when summarized by SOC and PT, AEs will be presented in decreasing frequency of PT within SOC across treatment arms. If more than 1 AE is recorded for a patient within any SOC or PT term, the patient will only be counted once on the most severe grade and the closest relationship to treatment.

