8.1.5. Committees

The following committees will be established to evaluate patients' safety and/or efficacy of the study treatment. There will be charters for these committees to follow.

Independent Data Monitoring Committee (iDMC)

The independent Data Monitoring Committee (iDMC) will be established to conduct interim efficacy and safety analyses as specified in Section 12.2.13 and will follow an approved iDMC charter. The iDMC may initiate a consultation with an appropriate expert (such as cardiac) if additional expertise is needed regarding evaluation of any safety signals. The iDMC will communicate back to Lilly Senior Management Designee (SMD) about their assessment.

The iDMC will also review adverse events of special interest (AESIs), including:

- myocardial failure, dysfunction
- myocardial ischemia or infarction
- arrhythmias
- cardiovascular insufficiency
- IRRs

The first iDMC meeting to review interim data for monitoring the loading dose will occur when approximately 80 patients (approximately 40 patients from each arm) have received 2 cycles of treatment or discontinued all study treatment due to any reasons prior to Day 8 in Cycle 2.

Subsequent iDMC meetings will occur approximately every 6 months thereafter. Enrollment and treatment will continue during the iDMC safety assessments. In the event a safety signal is detected, additional meetings may occur as needed. See Section 12.2.13 for additional details.

Independent Review Committee (IRC)

An Independent Review Committee (IRC) may review the CT scans and MRI scans for tumor assessments from selected patients if necessary (for example, based on inquiries from regulatory authorities).

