9.4.1.1.2. Doxorubicin

9.4.1.1.2.1. Hematologic Toxicity

Doxorubicin will not be administered after the initial dose if the patient's ANC is <1000 cells/ μL or if the platelet count is $<100,000$ cells/ μL . When necessary, the next treatment cycle should be delayed until the ANC is ≥ 1000 cells/ μL and the platelet count is $\geq 100,000$ cells/ μL and nonhematologic toxicities have resolved. For patients who experience \geq Grade 3 neutropenic fever or infection or Grade 4 neutropenia without fever lasting more than 1 week, doxorubicin should be reduced to 75% of the starting dose (that is, to approximately 60 mg/m²). If a patient experiences a second incidence of neutropenic fever/infection or has another episode of Grade 4 neutropenia lasting >1 week, then a second dose reduction to 45 mg/m² will be necessary. Therapeutic and prophylactic use of Neulasta[®] (pegfilgrastim) or other G-CSFs will be allowed per current American Society of Clinical Oncology (ASCO; Smith et al. 2006) and National Comprehensive Cancer Network (NCCN) guidelines (NCCN 2014). For patients with Grade 4 ANC without fever/infection lasting less than 1 week, retreatment will be allowed at the investigator's discretion with the full dose of doxorubicin (75 mg/m²) with recommended use of G-CSFs per current ASCO guidelines (Smith et al. 2006). See [Table JGDJ.4](#) for doxorubicin dose modification for neutropenia.

Table JGDJ.4. General Guidelines for Doxorubicin Dose Modification Due to Neutropenia

Toxicity	Required Dose Modification
ANC <1000 cells/ μ L	No doxorubicin administered; treatment cycle delayed.
At retreatment:	
If \geq Grade 3 neutropenic fever/infection has occurred	Approximately 60 mg/m ² doxorubicin.
If Grade 4 neutropenia lasting longer than 1 week has occurred	Approximately 60 mg/m ² doxorubicin.
Grade 4 absolute neutrophil count (ANC) without fever/infection	Retreatment with doxorubicin at full dose at investigator's discretion with recommended use of prophylactic G-CSFs.
Second incidence of either:	Second dose reduction to 45 mg/m ² .
1) \geq Grade 3 neutropenic fever/infection	
2) Grade 4 neutropenia lasting longer than 1 week	

9.4.1.1.2.2. Cardiovascular Toxicity

Cardiotoxicity is a recognized risk of doxorubicin that increases with higher cumulative drug exposure. Cardiac monitoring is conducted by a combination of monitoring of clinical parameters, ECG, and echocardiogram (ECHO) / multigated acquisition (MUGA) scan.

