10.3.1.3. Adverse Events of Special Interest (AESI)

Adverse events of special interest are events that have been identified as safety signals during preclinical or early clinical trials or based on class effects of similar drugs. These events will be monitored prospectively in the clinical developmental program. Each event is defined by a careful assessment and grouping of individual related MedDRA preferred terms.

AESI for olaratumab/placebo

Infusion-related reactions

AESIs for combination of olaratumab/placebo and doxorubicin

Infusion-related reactions

Cardiac arrhythmias and cardiac dysfunction

Refer to Section 9.4.1.1 for special treatment considerations for dose delay, modifications, and discontinuations from olaratumab/placebo and doxorubicin, including adverse events of concern or special interest.

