10.3.3. Safety Monitoring

The Sponsor will monitor blinded safety data throughout the course of the study.

Lilly will review SAEs within time frames mandated by company procedures. The Lilly CRP will, as is appropriate, consult with the functionally independent Global Patient Safety therapeutic area physician or clinical scientist, and review:

- trends in safety data
- laboratory analytes
- adverse events, including cardiac events such as:
 - myocardial failure, dysfunction
 - myocardial ischemia or infarction
 - arrhythmias
 - cardiovascular insufficiency
- adverse events of special interest (as defined in Section [10.3.1.3](#))

If a patient experiences elevated alanine aminotransferase (ALT) $> 5 \times$ ULN and elevated total bilirubin $> 2 \times$ ULN, clinical and laboratory monitoring should be initiated by the investigator. For patients entering the study with ALT $> 3 \times$ ULN, monitoring should be triggered at ALT $> 2 \times$ baseline. Details for hepatic monitoring depend upon the severity and persistence of observed laboratory test abnormalities. To ensure patient safety and comply with regulatory guidance, the investigator is to consult with the Lilly CRP regarding collection of specific recommended clinical information and follow-up laboratory tests. See [Attachment 3](#).

In the event that safety monitoring uncovers an issue that needs to be addressed by unblinding at the group level, only members of the data monitoring committee (an advisory group for this study formed to protect the integrity of data; refer to Section 12.2.13) can conduct additional analyses of the safety data.

For the purpose of this study, in which survival is a primary endpoint, all deaths and SAE reports will be reviewed in a blinded manner by Lilly during the clinical trial. These reports will be reviewed to assure completeness and accuracy but will not be unblinded to Lilly during the clinical trial. If a death or other clinical AE is deemed serious, unexpected, and possibly related to study treatments, only Lilly Global Patient Safety representatives external to the study team will be unblinded for regulatory reporting and safety monitoring purposes. These measures will preserve the integrity of the data collected during this trial and minimize any potential for bias while providing for appropriate safety monitoring.

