10.3.3.1. Cardiac Events of Special Interest

Patients exposed to doxorubicin are at risk for cardiovascular events. These events will be monitored throughout the JGDJ study as cardiac AESI. Each event is defined by a careful assessment and grouping of individual related MedDRA preferred terms.

1. Cardiac dysfunction
2. Arrhythmias

AESI data will be collected for all study treatment arms and monitored throughout the conduct of this study and across the development program. If cardiovascular events are reported, sites will be prompted to collect additional information.

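### Protocol 8.1.5 makes myocardial ischaemia or infarction an AESI for iDMC review, but the AESI definitions and the SAP Appendix 2 term list have no place for it, so the planned AESI tables give no pooled count

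*SAP*

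**What the plan says.** Protocol 8.1.5 sets out the iDMC's task: "The iDMC will also review adverse events of special interest (AESIs), including" five items. Four are cardiovascular: "myocardial failure, dysfunction"; "myocardial ischemia or infarction"; arrhythmias; and cardiovascular insufficiency. The fifth is infusion-related reactions (IRRs).

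The sections that define AESIs are narrower. Protocol 10.3.1.3 gives IRRs plus "Cardiac arrhythmias and cardiac dysfunction". Protocol 10.3.3.1 says of doxorubicin-related cardiovascular events, "These events will be monitored throughout the JGDJ study as cardiac AESI", and then numbers only dysfunction and arrhythmias. Protocol 10.3.3, on the sponsor's blinded review, repeats the four cardiac items of 8.1.5 under "adverse events, including cardiac events such as". It lists AESIs as defined in 10.3.1.3 as a separate item.

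SAP 5.2.1.2 and 5.14.2 follow the narrower definition, and 5.14.2 states that "The list of PTs for AESIs is in" Appendix 2. The groups feed the report tables in SAP 5.14.3 and the by-preferred-term AESI output for the iDMC in SAP 5.17.2.

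**The concern.** An AESI group exists to pool related preferred terms, so that a signal spread over several of them can be seen as one count per arm. If a category is assigned to the iDMC as an AESI but has no group and no terms, the AESI table shows nothing for it whatever the data contain. A reader who takes that table as the cardiac safety summary could read silence as absence.

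The same question arises for the heart-muscle injury expected from the backbone drug. Protocol 9.4.1.1.2.2 says "Cardiotoxicity is a recognized risk of doxorubicin that increases with higher cumulative drug exposure", and doxorubicin is planned in both arms. If the dysfunction group omits diagnoses that belong there, its count depends partly on which words the investigator chose.

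**Working it through.** No power or alpha figure is involved. The check sets the category lists side by side and then searches the terms in Appendix 2.

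**1. Categories**

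| Item in Protocol 8.1.5 | Protocol 10.3.1.3 / 10.3.3.1 | SAP 5.2.1.2 / 5.14.2 | SAP Appendix 2 |
|---|---|---|---|
| Myocardial failure or dysfunction | Cardiac dysfunction | Group | 72 entries |
| Arrhythmias | Arrhythmias | Group | 103 entries |
| IRRs | IRRs (10.3.1.3) | Group | 48 + 9 = 57 entries |
| Myocardial ischaemia or infarction | Absent | No group | No diagnosis term |
| Cardiovascular insufficiency | Absent | No group of that name | Partly covered by shock, low-output and failure terms |

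Total searched: 72 + 103 + 57 = 232 entries, counted as listed, including a few repeats. The block of 48 hypersensitivity terms has no heading in the text available. That may come from reading the PDF and does not affect the result.

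**2. Term search**

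| Text searched for | Entries found |
|---|---|
| isch, infarct, angina, coronary | 0 |
| cardiomyop, cardiotox | 0 |
| troponin, chest pain | 0 |
| myocard | 2: Myocardial depression; Scan myocardial perfusion abnormal (both under dysfunction) |
| ejection | 1: Ejection fraction decreased (dysfunction) |
| perfusion | 2: Scan myocardial perfusion abnormal (dysfunction); Reperfusion arrhythmia (arrhythmias) |
| Kounis | 1: Kounis syndrome (among the hypersensitivity terms) |

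None of the entries found is an ischaemia or infarction diagnosis in a cardiac group.

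**3. What the planned outputs would show**

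- *AESI outputs* (SAP 5.14.3 and 5.17.2): no pooled row for ischaemia or infarction. The cardiac AESI listing in 5.14.3 is likewise limited to arrhythmia and dysfunction.
- *Other iDMC outputs* (SAP 5.17.2): TEAEs, Grade 3 to 5 events and SAEs, listings of SAEs and of all AEs, and further analyses on request. Ischaemic events appear here. The TEAE and SAE tables are by preferred term.
- *Other report outputs* (SAP 5.14.2.2): TEAEs by system organ class and preferred term, and by high-level group term and high-level term. These pool related events, but they are not in the iDMC set listed in 5.17.2.

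**4. The dysfunction list**

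The list is broad. It includes cardiac failure in many forms, left ventricular and systolic dysfunction, cardiomegaly, peripheral oedema, heart transplant and even neonatal terms, although the trial enrols adults. A wish for a narrow, specific group therefore does not explain why cardiomyopathy and cardiotoxicity are absent. An event coded to left ventricular dysfunction would count. One coded only to a cardiomyopathy or cardiotoxicity term would not.

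**The case against.** The strongest reply is that the SAP did what the protocol's defining sections say. Sections 10.3.1.3 and 10.3.3.1 give the same groups as the SAP, and 10.3.3 treats ischaemia as a cardiac event apart from the defined AESIs. On that view 8.1.5 is the odd passage out. This stands as to origin: a reader might infer that the SAP departs from the protocol's AESI definition, and it does not. The conflict is inside the protocol, and the SAP inherits it.

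A reader might also infer that the iDMC will not see ischaemic events. The documents do not support that, given the other outputs in SAP 5.17.2. Section 8.1.5 requires review of the events and does not say it must be through an Appendix 2 table. The iDMC charter is a separate document and was not available.

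Other replies also stand:

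- Cardiomyopathy and cardiotoxicity are not in the 8.1.5 list. Exclusion criterion 21 uses cardiomyopathy for an illness at screening, not for doxorubicin injury. The omission is therefore an inference from the failure/dysfunction item in 8.1.5 and the risk stated in 9.4.1.1.2.2.
- It is tempting to say that doxorubicin's main toxicity is undercounted. That is not shown: it depends on how reports are coded and whether a listed term is reported alongside.
- Cardiovascular insufficiency should not be counted as a second missing category. Cardiogenic shock, low cardiac output syndrome and cardiopulmonary failure are listed.
- The possible dexrazoxane analysis in SAP 5.9 does not cite Appendix 2, so it cannot be said to inherit the gap.

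SAP 5.2.1.2 lets AESI categories change as knowledge grows. That permits the correction without making it, and ischaemia needs no new knowledge because 8.1.5 already names it.

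**Conclusion.** The point holds for the AESI tables. One of the four cardiac categories that Protocol 8.1.5 assigns to the iDMC has no AESI definition, no group and no diagnosis term, so its pooled count is missing from the planned AESI outputs. This part is direct from the text and rests only on Appendix 2 having been read completely.

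The lack of cardiomyopathy and cardiotoxicity terms is also a fact of the list. That they belong in the dysfunction group, and that the count could therefore depend on reported wording, is inference. The number of patients affected cannot be derived from the documents.

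What is missing is grouping, not data. The primary and key secondary efficacy analyses are untouched.

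**What to change.** 1. Use one set of AESI categories in Protocol 8.1.5, 10.3.1.3 and 10.3.3.1 and in SAP 5.2.1.2 and 5.14.2.
2. Add a Myocardial Ischaemia/Infarction group to SAP Appendix 2, with its preferred terms, to match 8.1.5. Deleting the item from 8.1.5 would make the texts agree but leave the iDMC without a pooled count.
3. Add cardiomyopathy and cardiotoxicity preferred terms to Cardiac Dysfunction.
4. Use the same list for the iDMC outputs in SAP 5.17.2 and the report tables and cardiac AESI listing in SAP 5.14.3.
5. Lock the list before the sponsor is unblinded. SAP 5.17 keeps the sponsor blinded until the final analyses, so the terms can be chosen without knowledge of results by arm.

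The cost is short wording changes in the protocol, an edit to the SAP and its appendix, and a rerun of the AESI programs. No new data are needed.
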